#### **B.5.5.1 Sample size rationale and statistical power**

The sample size estimate to determine primary endpoint is based on the primary objective of demonstrating superiority of the test group to the control group. Established methods were followed in determining the superiority criteria and the related sample size estimate

- Test basis: Pearson Chi-square binomial test for superiority
- Estimated responder rate of 60% in the test group and 30% in the control group
- Significance level, alpha, of 0.05 two-sided
- Randomization: 1:1
- A sample size of 50 subjects in each group will result in greater than 85% power for the study

Based on these assumptions, a minimum of 50 randomized subjects per treatment group (100 total) are required.

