#### **B.5.5.2 Overall Sample Size and Enrollment**

Based on the primary endpoint requirement, a minimum of 50 subjects per treatment group are required (100 total). To account for a combined estimated attrition of 33% for subjects that do not complete the Trial Phase, and subjects that exit study before the 6-month primary endpoint visit, approximately 150 subjects would need to be randomized.

To account for 50% attrition prior to randomization (including subject ineligibility after signing the informed consent and subject dropout), it is estimated that a total of up to 300 subjects would need to be enrolled in the study.

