### B.7.2. Effectiveness Assessment Definitions

- Primary Effectiveness Assessment: For test subjects who have a successful Trial Phase and receive a permanent implant, the Primary Efficacy Assessment occurs at the follow up visit 6 months after Device Activation. For subjects who do not have a successful Trial Phase (based on subject's pain score) or subjects who do not want a permanent device implant due to insufficient pain relief (based on subject's discontinuation reason), the Primary Efficacy Assessment occurs at the end of the Trial Phase. For control arm subjects, the Primary Efficacy Assessment occurs at the 6 months follow up visit post-randomization.

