5.7.1.2 Handling of Missing Data

For subjects in the DTM™ SCS arm who do experience an unsuccessful Trial Phase, also referred to as a **Trial Failure**, results (i.e., VAS back scores) from the Trial Phase will be utilized for the primary endpoint. Specifically, the Trial Phase results of subjects who failed the Trial Phase will be attributed for each time point throughout the study, as if they remained in the study.

Subjects who did not complete the Trial Phase due to withdrawal (e.g., an adverse event experienced during the Trial Phase, physician withdrawal due to non-compliance, withdrawal of consent, etc.), will not be included in the mITT analysis data set.

In the event of missing primary endpoint data among the mITT subjects either randomized to control or DTM™ SCS subjects who did complete the Trial Phase, the primary analysis for the primary endpoint will be conducted using multiple imputation (MI) methodology rather than the methods specified in Section 5.7.1.1. The specified Pearson Chi-square test will be presented for the observed data as a supporting analysis.

For the MI analysis each missing datum is replaced by multiple values in multiple datasets. The imputed datasets are then analyzed and combined for inference. Since the primary efficacy, and secondary efficacy endpoints, are based on the same underlying data of change in VAS, and vary only in the parameterization (continuous VAS vs. dichotomized responder) or value used for the null hypothesis, the same imputed data sets will be used for the analysis of each endpoint. Imputation will be performed separately by treatment group.

Statistical Analysis Plan		Page 10 of 14
Sponsor SGX International	Study EU RCT DTM SCS vs. CMM	Version 3.0

For each imputation model, covariates will include:

- Baseline variables: age (years), gender, number of year(s) since diagnosed with chronic back pain, unilateral versus bilateral pain, back pain VAS
- Follow-up variables: end of trial phase back pain VAS, follow-up back pain VAS (after device activation) from 1 month through 24 months. The imputation models employed will correspond to the hypothesis being tested, for the primary and secondary endpoints through 6 months, the models will use data through 6 months. For secondary endpoints post 6 months, the model will be extended to the relevant time point.

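### Test subjects who pass the trial but are never implanted stay in the primary analysis and are imputed at roughly the on-therapy response rate

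*SAP*

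**What the plan says.** **Who is analysed.** Protocol B.7.1 and SAP 5.2 define mITT, the primary set, as test subjects with a successful Trial Phase plus all randomized controls. Implantation is not required. Protocol B.6.7 implants only trial passers who agree to go on, up to 90 days after the trial ends, so a passer can remain without a device.

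**What a responder is.** Protocol B.7.3 and SAP 5.7.1 require at least a 50% fall in back pain VAS at 6 months after device activation (test) or after randomization (control).

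**Missing scores.** SAP 5.7.1.2 says that for mITT controls, and for DTM SCS "subjects who did complete the Trial Phase, the primary analysis for the primary endpoint will be conducted using multiple imputation (MI) methodology". It adds: "Imputation will be performed separately by treatment group". The listed predictors are baseline variables, end-of-trial VAS and post-activation VAS. None records whether the subject was implanted, explanted or switched off.

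**Decliners.** Protocol B.7.2 moves the primary assessment to the end of the Trial Phase for trial failures and also for "subjects who do not want a permanent device implant due to insufficient pain relief". SAP 5.7.1.2 and 5.7.2.1 apply trial scores to trial failures only.

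**Device loss.** Protocol B.6.20 allows withdrawal with explant, and B.6.21 lists adverse events among the reasons for withdrawal. SAP 5.4 counts implants and explants under disposition, but no section says how these events enter the primary endpoint.

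**The concern.** For a never-implanted subject, the 6-month post-activation score is not a value that exists and was missed. There was no activation, so the test-arm definition of response cannot be met. Imputation fills the gap with a score predicted from a trial result that is by definition at least 50% better than baseline, using relationships estimated in subjects on stimulation. The answer it gives is how the subject would have fared with a working device. The synopsis, in contrast, describes the endpoint as the share of randomized subjects who respond to SCS therapy at 6 months.

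The two documents also send the same person to different places. Take a subject who reaches 50% relief on VAS in the trial but declines the implant because relief is insufficient. Read literally, Protocol B.7.2 uses the end-of-trial score, which meets the response threshold. The SAP sends that subject to multiple imputation. Either route can credit response where no therapy is delivered.

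The supporting analyses would not expose this. The observed-data chi-square drops these subjects, the repeated-measures model in SAP 5.6 relies on missing at random, the Per-Protocol set leaves out never-implanted test subjects, and the missing-data sensitivity analyses promised in SAP 5.3 are not specified.

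**Working it through.** **1. The plan's own figure.** Protocol B.5.5.1 gives "Estimated responder rate of 60% in the test group and 30% in the control group", "Significance level, alpha, of 0.05 two-sided" and "Randomization: 1:1", and states: "A sample size of 50 subjects in each group will result in greater than 85% power for the study". With pooled variance under the null and n per arm,

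power = Φ{[p1 − p2 − 1.96·√(2·p̄(1 − p̄)/n)] / √([p1(1 − p1) + p2(1 − p2)]/n)}.

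With p1 = 0.60, p2 = 0.30, n = 50: (0.300 − 0.195)/0.0949 = 1.107, so power is 86.6%. Exact enumeration of the Pearson test gives 87.6%. The statement reproduces.

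**2. What the imputation does.** In a small regression-imputation simulation (VAS parameters assumed, about 50 trial passers, 5%, 10% or 20% missing at random, predictors baseline and end-of-trial VAS), imputed subjects responded at 64.8%, 63.7% and 63.5%. Implanted subjects with data responded at 64.8%, 64.0% and 64.4%. So imputed response is close to on-therapy response.

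**3. Size.** Let f be the share of mITT test subjects with no device and no 6-month score, and q the responder rate among treated subjects. The test rate is about q under imputation and q(1 − f) under a non-responder rule, a gap of f·q. If the true response of these subjects is 30%, the assumed control rate, the gap is f·(q − 0.30). The documents do not give f: Protocol B.5.5.2 offers only a "combined estimated attrition of 33% for subjects that do not complete the Trial Phase" together with exits before 6 months. The range 5% to 10% is an assumption. I take q = 0.60 from the planning rate.

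| f | Imputed | Non-responder rule | Gap f·q | Gap if true response is 30% |
|---|---|---|---|---|
| 5% | 60% | 57.0% | 3.0 points | 1.5 points |
| 10% | 60% | 54.0% | 6.0 points | 3.0 points |

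Per 50 subjects, f·q is 1.5 to 3.0 expected imputed responders. With f = 2% the gap is 1.2 points. With q = 80% (the 3-month DTM rate in Protocol B.1) and f of 5% to 10%, it is 4 to 8 points.

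**4. When it could change the result.** Treat expected counts as observed, with 15/50 responders in control. The planned 30/50 in test gives p = 0.0026, and 27/50 still gives p = 0.015. At 25/50, p = 0.041; at 24/50, p = 0.065. The rule matters for the test only near the threshold, but it always moves the reported rate.

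**5. Power under a non-responder rule.** With q = 0.60 and 50 per arm, the formula in step 1 gives 78.6% at p1 = 0.57 and 68.6% at p1 = 0.54. With q = 80% power stays above 99% for these f.

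**The case against.** Several stronger readings are tempting, and the documents do not support them.

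- **People without a device are scored as device responders.** Multiple imputation assigns a probability of response, not responder status.
- **Explanted subjects are treated as if still on therapy.** No text says so. If they attend at 6 months, their actual VAS is used. If they leave earlier, their own post-activation scores enter the model, and poor ones lower the imputed response. For them the issue is the missing-at-random assumption and the absence of a rule.
- **The control arm has no counterpart.** SAP 5.7.1.2 imputes control dropouts too, within their own arm. The net bias depends on dropout in both arms, which is not given.
- **Crossovers set a precedent.** Crossover follows an observed 6-month result of less than 50% relief (Protocol B.6.1). The rule counting crossovers as failures in SAP 5.7.2 concerns later visits.
- **Protocol B.7.2 declares decliners responders.** It fixes the time of assessment and groups them with trial failures, whom the synopsis counts as non-responders. Responder credit for one who passed on VAS is a literal consequence, not a stated intention, and the group is probably small.
- **The inflation could be put against 75 randomized test subjects and zero response.** The primary set is mITT, not all 75. Test subjects also receive CMM, for which the plan assumes 30% response, so part of a gap measured against zero is a choice of estimand.

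It can also fairly be said that a composite non-responder strategy is one choice among several and that the plan does not commit to it for these events. That stands. What also stands is that the present rule imputes an outcome the endpoint's own definition cannot assign to a never-activated subject.

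**Conclusion.** The concern holds in a limited form. Never-implanted trial passers remain in mITT and are imputed at about the on-therapy rate. Early exits after explant, for lack of effect or for an adverse event have no endpoint rule and default to missing at random. Protocol B.7.2 and SAP 5.7.1.2 and 5.7.2.1 disagree on decliners and must be reconciled.

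The effect is 3 to 6 points on the test responder rate against a non-responder rule, and about half that if these subjects truly respond at 30%, set against a planned difference of 30 points. This rests on an assumed 5% to 10% affected and 60% imputed response. At 2% affected or less it is minor. It does not by itself threaten a result of the planned size, but it favours the test arm for the never-implanted group and could decide a close result. It should be settled before the analysis.

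**What to change.** In SAP 5.7.1.2, with a matching line in Protocol B.7.2 and in SAP 5.7.2.1:

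1. Count as non-responders the trial passers who do not receive an implant because of insufficient relief, an adverse event or their own choice.
2. In both arms, count as non-responders the subjects who leave before 6 months for lack of effect or a treatment-related adverse event, including withdrawal with explant, and have no 6-month score.
3. Use the observed 6-month score whenever there is one, whatever the device status. Do not base the rule on stopping assigned therapy: CMM may be modified at any time (Protocol B.4), so that has no clear meaning in control.
4. Reserve multiple imputation for missed visits and loss unrelated to therapy. Keep the current imputation as a named sensitivity analysis.

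**Cost.** The change is wording, using the discontinuation reason already recorded on the termination form (Protocol B.6.21). The price is a somewhat lower test responder rate and lower power: with 60% response among treated subjects and 50 per arm, about 79% if 5% are affected and 69% if 10% are, against 86.6% now. The sponsor should state whether the planned 60% refers to treated subjects or already allows for these failures, and recheck the stated power accordingly.

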5.7.2 Secondary Endpoints

The following secondary endpoints will be evaluated:

- If the primary efficacy endpoint in the test group is found to be superior to that in the control group, then a secondary endpoint will evaluate whether the proportion of subjects who achieve a 50% improvement in their back pain VAS score at 1, 3, 9, 12, 18 or 24 months in the test group is superior to that in the control group. A superiority test based on the difference in proportions will be performed based on the following null hypothesis, with a two-sided p-value of 0.05 or less considered evidence of statistical significance. A separate hypothesis test will be conducted for each time point.

Statistical Analysis Plan		Page 11 of 14
Sponsor	Study	Version
SGX International	EU RCT DTM SCS vs. CMM	3.0

H_0 : The proportion of subjects (P) who achieve a 50% improvement in their back pain VAS score at 1, 3, 9, 12, 18, or 24 months in the Test group is less than or equal to that in the Control group.

$$P_{\text{Test}} = P_{\text{Control}}$$

H_1 : The proportion of subjects (P) who achieve a 50% improvement in their back pain VAS score at 1, 3, 9, 12, 18, or 24 months in the Test group is greater than that in the Control group.

$$P_{\text{Test}} \neq P_{\text{Control}}$$

- Change in mean VAS will be evaluated with two-sample t-test of non-inferiority in means with a 0.65 cm non-inferiority margin at 6 months.

H_0 : The change (C) in subject's VAS pain intensity score relative to baseline at the Primary Efficacy Assessment in the Test group is worse than that of subjects in the Control group by more than 0.65 cm.

$$C_{\text{Test}} \geq C_{\text{Control}} + 0.65 \text{ cm}$$

H_1 : The change (C) in subject's VAS pain intensity score relative to baseline at the Primary Efficacy Assessment in the Test group is no more than 0.65 cm worse than the mean change from baseline in the control group.

$$C_{\text{Test}} < C_{\text{Control}} + 0.65 \text{ cm}$$

The non-inferiority margin of 0.65 cm was selected based on a previous study of a similar therapy against traditional SCSⁱ. In that study, the experimental therapy showed a 4.9 point improvement while traditional SCS showed a 3.6 point improvement for a difference of 1.3 points. Taking 50% of this treatment effect yields the margin of 0.65 cm. If the null hypothesis is successfully rejected for the non-inferiority test, a test for superiority of treatment to control will be performed based on a two-sided 0.05 alpha level.

The following secondary endpoints do not have an associated hypothesis, and no significance level will be assigned to statistical tests that may be performed.

- Comparison of Back Pain Treatment Success (responder rate), measured as subjects with at least a 50% reduction in Back Pain VAS, between test and control
- Comparison of mean change from Baseline in Back Pain VAS, between test and control.

Repeated measures models will be used to produce estimates for these two secondary endpoints, with graphical presentation of the responder rates and mean changes from baseline.

Analysis of results through 6 months will be based on the mITT population. For time points after 6 months where crossover is allowed, crossover subjects will be counted as failures (i.e. non-responders) for endpoints defined in terms of responders, carrying forward the baseline (pre-treatment). Sensitivity

Statistical Analysis Plan		Page 12 of 14
Sponsor SGX International	Study EU RCT DTM SCS vs. CMM	Version 3.0

analysis of both secondary endpoints will also be performed to where crossover subjects are censored at the point of crossover.

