#### B.7.4. Secondary Endpoints

The following secondary endpoints will be evaluated:

- Comparison of the percentage of Individual Responders between the test and control groups in a statistical test of superiority over time. In addition, data will be summarized at the individual time points at 1 month, 3 months, 6 months, 9 months, 12 months, 18 months, and 24 months.
- Comparison of change from Baseline in VAS back pain score between test and control in statistical tests of non-inferiority and superiority at 1 month, 3 months, 6 months, 9 months, 12 months, 18 months, and 24 months . This is calculated as: Change from Baseline in Back Pain VAS = Follow-up Visit Pain VAS – Baseline Pain VAS. A negative result reflects a decrease in the Pain VAS, while a positive result reflects an increase in Pain VAS.

Analysis of results through 6 months will be based on the mITT population. Sensitivity analysis of both secondary endpoints will also be performed to assess the impact of crossover.

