### B.9.2.2 Secondary Analyses

The following *secondary endpoints* will be evaluated:

- If the primary efficacy endpoint in the test group is found to be superior to that in the control group, then a secondary endpoint will evaluate whether the proportion of subjects who achieve a 50% improvement in their back pain VAS score at 1, 3, 9, 12, 18 or 24 months in the test group is superior to that in the control group. A superiority test based on the difference in proportions will be performed based on the following null hypothesis, with a two-sided p-value of 0.05 or less considered evidence of statistical significance.

$H_0$ : The proportion of subjects (P) who achieve a 50% improvement in their back pain VAS score at 1, 3, 9, 12, 18, or 24 months in the Test group is less than or equal to that in the Control group.

$$P_{\text{Test}} = P_{\text{Control}}$$

$H_1$ : The proportion of subjects (P) who achieve a 50% improvement in their back pain VAS score at 3 months in the Test group is greater than that in the Control group.

$$P_{\text{Test}} \neq P_{\text{Control}}$$

- Change in mean VAS will be evaluated with two-sample t-test of non-inferiority in means with a 0.65 cm non-inferiority margin at 6 months.

$H_0$ : The change (C) in subject's VAS pain intensity score relative to baseline at the Primary Efficacy Assessment in the Test group is worse than that of subjects in the Control group by more than 0.65 cm.

$$C_{\text{Test}} \geq C_{\text{Control}} + 0.65 \text{ cm}$$

$H_1$ : The change (C) in subject's VAS pain intensity score relative to baseline at the Primary Efficacy Assessment in the Test group is no more than 0.65 cm worse than the mean change from baseline in the control group.

$$C_{\text{Test}} < C_{\text{Control}} + 0.65 \text{ cm}$$

The non-inferiority margin of 0.65 cm was selected based on a previous study of a similar therapy against traditional SCS. In that study, the experimental therapy showed a 4.9 point improvement while traditional SCS showed a 3.6 point improvement for a difference of 1.3 points. Taking 50% of this treatment effect yields the margin of 0.65 cm. If the null hypothesis is successfully rejected for the non-inferiority test, a test for superiority of treatment to control will be performed based on a two-sided 0.05 alpha level.

The following secondary endpoints do not have an associated hypothesis, and no significance level will be assigned to statistical tests that may be performed.

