5.1.3 Statistical Significance

Unless otherwise specified, hypothesis testing will be performed at the two-sided 0.05 significance level. P-values will be rounded to three decimal places. If a p-value is less than 0.001 it will be reported as "<0.001". If a p-value is greater than 0.999, it will be reported as ">0.999".

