5.7.1.1 Primary Analysis

The *primary efficacy endpoint* will be evaluated with a Pearson Chi-square binomial test for superiority at the two-sided 0.05 alpha level.

H_0 : The percentage of subjects (P) who achieve a 50% improvement in their back VAS pain score at 6 months in the Test group is the same as in the Control group.

$$P_{\text{Test}} = P_{\text{Control}}$$

H_1 : The percentage of subjects (P) who achieve a 50% improvement in their back VAS pain score at 6 months in the Test group is superior to that in the Control group.

$$P_{\text{Test}} \neq P_{\text{Control}}$$

Primary analysis will be based on the mITT analysis set.

In addition to the results from the hypothesis test, the numerator and denominator and percentage responders will be presented.

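### Six secondary responder tests, gated on the primary, are each called significant at 0.05 with no order or adjustment among them

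*SAP*

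**What the plan says.** The primary endpoint, the 6-month responder rate, is "evaluated with a Pearson Chi-square binomial test for superiority at the two-sided 0.05 alpha level" (SAP 5.7.1.1). The secondary responder tests begin with a gate, "If the primary efficacy endpoint in the test group is found to be superior to that in the control group" (SAP 5.7.2). Behind it the plan asks whether the responder rate "at 1, 3, 9, 12, 18 or 24 months in the test group is superior to that in the control group", "with a two-sided p-value of 0.05 or less considered evidence of statistical significance". The SAP adds: "A separate hypothesis test will be conducted for each time point". That sentence is not in Protocol B.9.2.2, which otherwise has the same gate, visits and threshold.

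The only general rule on error is in SAP 5.1.3: unless otherwise specified, "hypothesis testing will be performed at the two-sided 0.05 significance level". Neither document gives an order, an alpha split or an adjustment among the six visits.

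The SAP does have a descriptive category. After the six tests and the 6-month mean-change test, it lists further secondary items that have no hypothesis and no assigned significance level. The six responder tests stand outside that list. Protocol B.8.2 (Definition of Success) sets no success criterion beyond the primary.

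The documents also differ on how many tests there are:

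- **Responder rate.** Protocol B.7.4 describes a superiority test over time, with individual visits summarised. The SAP runs one test per visit.
- **VAS change.** Protocol B.7.4 plans comparisons "in statistical tests of non-inferiority and superiority at 1 month, 3 months, 6 months, 9 months" and on to 24 months, seven visits in all. Protocol B.9.2.2 has only "Change in mean VAS will be evaluated with two-sample t-test of non-inferiority in means with a 0.65 cm non-inferiority margin at 6 months", followed by superiority at 0.05, and the SAP agrees. Neither text says that this test is gated on the primary.

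**The concern.** A gate on the primary controls entry to the secondary family. It does not control error among the six tests once they are opened. The plan writes hypotheses for these six visits, attaches a significance threshold to each, and separates them from the items it treats as descriptive. A reader of the report may therefore take any one significant visit as a controlled result.

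The exposed case is a treatment that works at 6 months but not at some other visits, for example one whose effect does not last. The gate is then very likely to open, and each null visit offers another chance of a false claim. At stake are the onset and durability statements in the report, not the trial's primary conclusion.

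**Working it through.** **Inputs from the documents.** Six tests at two-sided 0.05, opened only if the primary is superior (SAP 5.7.2). Primary: 60% versus 30%, 50 per group, two-sided 0.05, power above 85% (SAP 4).

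**Assumption.** The documents give no correlation between the test statistics at different visits. I take a common value r for all seven, primary included, and vary it from 0 to 0.9.

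**Step 1: reproduce the plan's power, which is the chance that the gate opens.** With the pooled rate 0.45:

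- standard error under the null = √(2 × 0.45 × 0.55 / 50) = 0.0995
- standard error under the alternative = √((0.60 × 0.40 + 0.30 × 0.70) / 50) = 0.0949
- power = Φ((0.30 − 1.96 × 0.0995) / 0.0949) = Φ(1.107) = 86.6%

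Exact enumeration of the Pearson test gives 87.6%. Both agree with the stated figure. The primary statistic therefore has mean about 1.96 + 1.107 = 3.07.

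**Step 2: independent tests, six other visits null, 6-month effect real.**

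- Any false significant visit, ignoring the gate: 1 − 0.95⁶ = 26.5%. With the gate: 0.265 × 0.866 = 22.9%.
- Favouring the device, ignoring the gate: 1 − 0.975⁶ = 14.1%. With the gate: 0.141 × 0.866 = 12.2%.

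**Step 3: correlated tests.** Write each null statistic as √r·F + √(1−r)·e, with a shared standard normal F. Given F, let q be the chance that one visit is not falsely significant and g the chance that the gate opens. The error is the average over F of (1 − q⁶)·g. A simulation of 1,000,000 draws agrees to within about 0.1 percentage point.

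| Assumed r | Any false visit, no gate | Any false visit, gated | Favouring device, gated (nominal 2.5%) | Only 9–24 months null, any false visit, gated |
|---|---|---|---|---|
| 0 | 26.5% | 22.9% | 12.2% | 16.1% |
| 0.5 | 20.7% | 15.9% | 10.3% | 11.8% |
| 0.7 | 16.4% | 11.0% | 8.2% | 8.5% |
| 0.9 | 10.8% | 5.7% | 5.4% | 4.9% |

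As multiples of nominal, the gated two-sided error runs from 22.9/5 = 4.6 down to 5.7/5 = 1.1. The device-favouring error runs from 12.2/2.5 = 4.9 down to 5.4/2.5 = 2.2.

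**Step 4: no effect at any visit.** The gate then opens only by chance. The chance of a false primary result followed by at least one false secondary result is 1.3% at r = 0, rising to about 4.4% at r = 0.9. It stays below 5%.

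**Step 5: effect of an adjustment.** For six null tests, Holm's chance of any false rejection equals Bonferroni's, with the smallest p-value compared with 0.05/6 = 0.0083. Without counting the gate this is 4.9%, 4.1% and 3.3% at r = 0, 0.5 and 0.7. A fixed sequence gives 5.0%. Power for a single 60% versus 30% comparison with 50 per arm falls from 86.6% at 0.05 to 65.4% at 0.0083.

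**The case against.** **No success claim rests on these tests.** Protocol B.8.2 (Definition of Success) says so, and this is a post-market study of a CE-marked device. Neither document promises a family-wise level for the secondaries; the 0.05 is per test, and each test keeps it. This stands and limits the severity. It does not make the six tests descriptive, because the SAP has a category without significance levels and leaves them out of it.

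**The tests are positively correlated.** They reuse the same subjects' VAS scores. Crossover requires less than 50% relief (Protocol B.6.1), and crossover subjects then count as non-responders at every later visit (SAP 5.7.2). At the planned rates, up to 70% of controls and 40% of test subjects would meet the pain criterion for crossover, though dissatisfaction and the investigator's agreement are also needed. Late results thus partly repeat 6-month status, and a true null at 9 to 24 months would need test responders to lapse enough to offset the controls fixed as failures. This stands too: the low-correlation rows are upper values, and ordering or adjusting the tests does nothing about the crossover rule. At r = 0.9 the two-sided excess is slight, but the device-favouring error is still about twice nominal.

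**Stronger readings.** A reader might infer that the secondary tests have no hierarchy, or that the trial's false-positive rate is 26%. The documents support neither. The gate is a hierarchical step that controls the case of no effect anywhere, and 26.5% ignores it and assumes independence. The error of the primary conclusion does not change.

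**Conclusion.** The point holds in a limited form. Family-wise error among the six responder tests is not controlled once the primary has succeeded. The excess arises when the 6-month effect is real and several other visits are null. It is then roughly 6% to 23% two-sided, and 5% to 12% in the device's favour against a nominal 2.5%. These figures rest on the planned rates, 50 per arm, a common correlation assumed between 0 and 0.9, and all six visits null; with fewer null visits they are smaller. The inconsistency over the number of tests is a matter of text and needs no assumption. This should be corrected, but it does not threaten the primary analysis.

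**What to change.** 1. In SAP 5.7.2 and Protocol B.9.2.2, keep the gate and then either apply Holm across the six responder tests at overall two-sided 0.05, or state a fixed sequence and justify its order. Alternatively, report the visits as estimates with confidence intervals and remove the significance wording.
2. If a fixed sequence is chosen, consider what an early miss would block. Protocol B.6.16 exempts the 1-month visit from its four-week no-intervention rule, so placing that visit early could cost every later claim.
3. State whether the 6-month mean-change superiority test is gated on the primary and belongs to the same family. If it does, Holm's first step becomes 0.05/7 = 0.0071.
4. Reconcile Protocol B.7.4 with B.9.2.2 and the SAP: one responder test over time or six by visit, and VAS-change tests at seven visits or at 6 months only.

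The cost is a few sentences in each document, with no new data or subjects. Some visits may lose a formal significance claim: at Holm's strictest step, power for a single 60% versus 30% comparison falls from about 87% to 65%. A fixed sequence keeps the full 0.05 at its first step but loses every visit after the first miss.
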